6.3.11 Deaths

All deaths that occur during the study, or within the protocol defined 30-day follow-up period after the administration of the last dose of study treatment, must be reported as follows:

- Death clearly the result of disease progression should be reported to the study monitor at the next monitoring visit and should be documented in the DEATH eCRF but should not be reported as an SAE.
- Where death is not due (or not clearly due) to progression of the disease under study, the AE causing the death must be reported to the study monitor as an SAE within 24 hours (see Section 6.4) for further details. The report should contain a comment regarding the co-involvement of progression of disease, if appropriate, and should assign main and contributory causes of death. This information can be captured in the death eCRF.
- Deaths with an unknown cause should always be reported as an SAE. A post mortem maybe helpful in the assessment of the cause of death, and, if performed, a copy of the post mortem results should be forwarded to AstraZeneca within the usual timeframes.

6.4 Reporting of SAEs

All SAEs have to be reported, whether or not considered causally related to the IP, or to the study procedure(s). All SAEs will be recorded in the CRF.

If any SAE occurs in the course of the study, then Investigators or other site personnel inform the appropriate AstraZeneca representatives within one day ie, immediately but **no later than 24 hours** of when he or she becomes aware of it.

The designated AstraZeneca representative works with the Investigator to ensure that all the necessary information is provided to the AstraZeneca Patient Safety data entry site **within**

1 calendar day of initial receipt for fatal and life threatening events **and within 5 calendar days** of initial receipt for all other SAEs.

For fatal or life-threatening AEs where important or relevant information is missing, active follow-up is undertaken immediately. Investigators or other site personnel inform AstraZeneca representatives of any follow-up information on a previously reported SAE within one calendar day ie, immediately but **no later than 24 hours** of when he or she becomes aware of it.

Once the Investigators or other site personnel indicate an AE is serious in the Clinical Database, an automated email alert is sent to the designated AstraZeneca representative.

If the Clinical Database is not available, then the Investigator or other study site staff reports an SAE to the appropriate AstraZeneca representative by telephone.

The AstraZeneca representative will advise the Investigator/study site staff how to proceed.

The reference document for definition of expectedness/listedness is the IB for the AstraZeneca drug and the EU Summary of Product Characteristics, USPI or other local label for the active comparator products (including any AstraZeneca comparator).

Regulatory Reporting Requirements for SAEs

Prompt notification by the investigator to the sponsor of a SAE is essential so that legal obligations and ethical responsibilities towards the safety of participants and the safety of a study intervention under clinical investigation are met.

The sponsor has a legal responsibility to notify both the local regulatory authority and other regulatory agencies about the safety of a study intervention under clinical investigation. The sponsor will comply with country-specific regulatory requirements relating to safety reporting to the regulatory authority, Institutional Review Boards (IRB)/Independent Ethics Committees (IEC), and investigators.

For all studies except those utilizing medical devices investigator safety reports must be prepared for suspected unexpected serious adverse reactions (SUSAR) according to local regulatory requirements and sponsor policy and forwarded to investigators as necessary.

An investigator who receives an investigator safety report describing a SAE or other specific safety information (e.g., summary or listing of SAEs) from the sponsor will review and then file it along with the Investigator's Brochure or and will notify the IRB/IEC, if appropriate according to local requirements.

6.5 Overdose

There is currently no specific treatment in the event of overdose with olaparib ceralasertib or AZD1775 and possible symptoms of overdose are not established.

To date, there has been one patient who has experienced an overdose with AZD1775 which was associated with AEs.

Olaparib, ceralasertib, and AZD1775 must only be used in accordance with the dosing recommendations in this protocol. Any dose or frequency of dosing that exceeds the dosing regimen specified in this protocol should be reported as an overdose.

Adverse reactions associated with overdose should be treated symptomatically and should be managed appropriately.

- An overdose with associated AEs is recorded as the AE diagnosis/symptoms on the relevant AE modules in the CRF and on the Overdose CRF module.
- An overdose without associated symptoms is only reported on the Overdose CRF module.

If an overdose on an AstraZeneca study drug occurs in the course of the study, then the Investigator or other site personnel inform appropriate AstraZeneca representatives immediately, or **no later than 24 hours** of when he or she becomes aware of it.

The designated AstraZeneca representative works with the Investigator to ensure that all relevant information is provided to the AstraZeneca Patient Safety data entry site.

For overdoses associated with an SAE, the standard reporting timelines apply, see Section 6.4. For other overdoses, reporting must occur within 30 days.

6.6 Pregnancy

All pregnancies and outcomes of pregnancy should be reported to AstraZeneca except for:

- If the pregnancy is discovered before the study patient has received any study drug.

6.6.1 Maternal exposure

If a patient becomes pregnant during the course of the study all IPs should be discontinued immediately.

The outcome of any conception occurring from the date of the first dose of study medication until 1 month after the last dose of study medication must be followed up and documented.

Pregnancy itself is not regarded as an AE unless there is a suspicion that the IP under study may have interfered with the effectiveness of a contraceptive medication. Congenital abnormalities/birth defects and spontaneous miscarriages should be reported and handled as

SAEs. Elective abortions without complications should not be handled as AEs. The outcome of all pregnancies (spontaneous miscarriage, elective termination, ectopic pregnancy, normal birth or congenital abnormality) should be followed up and documented even if the patient was discontinued from the study.

If any pregnancy occurs from the date of the first dose of study medication until 1 month after the last dose of study medication, then the Investigator or other site personnel informs the appropriate AstraZeneca representatives within 1 day ie, immediately but **no later than 24 hours** of when he or she becomes aware of it.

The designated AstraZeneca representative works with the Investigator to ensure that all relevant information is provided to the AstraZeneca Patient Safety data entry site within 1 or 5 calendar days for SAEs (see Section 6.4) and within 30 days for all other pregnancies.

The same timelines apply when outcome information is available.

The PREGREP module in the CRF is used to report the pregnancy and the PREGOUT is used to report the outcome of the pregnancy.

6.6.2 Paternal exposure

Male patient should refrain from fathering a child or donating sperm during the study and for 6 months following the last dose.

Pregnancy of the patient's partners is not considered to be an AE. However, the outcome of all pregnancies (spontaneous miscarriage, elective termination, ectopic pregnancy, normal birth or congenital abnormality) should if possible be followed up and documented. To capture information about a pregnancy from the partner of a male patient, the male patient's partner consent must be obtained to collect information related to the pregnancy and outcome; the male patient should not be asked to provide this information. The outcome of any conception occurring should be followed up and documented.

The outcome of any conception occurring from the date of the first dose until 3 months *after the last dose* should be followed up and documented.

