11. Women of childbearing potential and their partners, who are sexually active, must agree to the use of 2 highly effective forms of contraception in combination (as described in [Appendix E](#)) from the signing of the informed consent, throughout the period of taking study treatment and for at least 1 month after last dose of study drug(s), or they must totally/truly abstain from any form of sexual intercourse (as described in [Appendix E](#)).
12. Male patients must use a condom during treatment and for 6 months after the last dose of study drug(s) when having sexual intercourse with a pregnant woman or with a woman of childbearing potential. Female partners of male patients should also use a highly effective form of contraception (see [Appendix E](#) for acceptable methods) for 6 months after the last dose of study drug(s) if they are of childbearing potential.
13. Patient is willing and able to comply with the protocol for the duration of the study including undergoing treatment and scheduled visits and examinations.
14. * Patients must have a life expectancy of ≥ 16 weeks.

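### Section 6.6.2 stops its only timed follow-up of partner-conception outcomes at 3 months after the last dose, while the male precaution period is 6 months throughout the protocol

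*Protocol*

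**What the plan says.** Section 6.6.2 begins with the restriction on male patients: "Male patient should refrain from fathering a child or donating sperm during the study and for 6 months following the last dose". It then deals with partner pregnancies in three sentences.

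- The outcome of all such pregnancies "should if possible be followed up and documented". No time limit is given.
- After the requirement for the partner's consent: "The outcome of any conception occurring should be followed up and documented". Again there is no time limit.
- The closing sentence: "The outcome of any conception occurring from the date of the first dose until 3 months" after the last dose is to be followed up and documented.

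The parent section 6.6 has a general rule, also untimed: "All pregnancies and outcomes of pregnancy should be reported to AstraZeneca". Its one exception is a pregnancy discovered before any study drug has been taken.

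In the female counterpart, section 6.6.1, outcomes of conceptions from the first dose "until 1 month after the last dose of study medication must be followed up and documented".

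**The concern.** Section 6.6.2 gives two rules for the same event. A partner conception in month 5 after the last dose falls under the untimed sentences and outside the timed one. The timed limit is also half the length of the period, set a few lines earlier, in which the protocol tells the patient not to father a child.

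What is at stake is even safety follow-up. A site that takes 3 months as the limit would not document the outcome of a conception in months 4 to 6. A site that follows the untimed wording would. The protocol treats this exposure as a real one: Appendix E puts olaparib in a medium-to-high foetal risk class, and section 1.3.3 includes reproductive and genetic toxicity among the potential risks of ceralasertib. Men are eligible under inclusion criterion 2.

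**Working it through.** No power, alpha or event count is involved. The check compares every current statement of a post-treatment period for men with the follow-up window, and then does the same for women. Three-month male figures in the version history describe superseded text and are not counted.

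**Male post-treatment period in the current protocol**

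| Place | Subject | Period after last dose | Statements |
|---|---|---|---|
| 3.1, inclusion criterion 12 | condom use; partner contraception | 6 months | 2 |
| 3.7.2 | condom use; sperm donation; sperm freezing advice | 6 months | 3 |
| 6.6.2, first sentence | fathering a child or donating sperm | 6 months | 1 |
| Appendix E | condom use; sperm donation; abstinence | 6 months | 3 |
| 6.6.2, last sentence | follow-up of conception outcomes | 3 months | 1 |

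Statements at 6 months: 2 + 3 + 1 + 3 = 9. Statements at 3 months: 1.

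**Restriction period minus timed follow-up window**

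- Male: 6 − 3 = 3 months. Months 4 to 6 rest on the untimed sentences alone.
- Female: 1 − 1 = 0 months. The restriction comes from inclusion criterion 11 and the window from 6.6.1.

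**How many patients could be involved**

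The documents give no proportion of men. As an assumption with no source, take 1% to 5% of the roughly 350 randomised patients in section 8.2:

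- 1%: 0.01 × 350 = 3.5, about 4 men.
- 5%: 0.05 × 350 = 17.5, about 18 men.

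This counts men, not conceptions. The affected unit is a partner conception in months 4 to 6, with partner consent, during a period when condoms and partner contraception are required. The documents offer no way to estimate that number, and it should be well below the number of men.

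**The case against.** The strongest reply is that nothing is lost. The sentence just before the timed one covers any conception, an earlier one covers all pregnancies where possible, and 6.6 requires all pregnancies and outcomes to be reported. The timed sentence does not say that follow-up ends at 3 months. Read together, months 4 to 6 are covered. This is correct as a literal reading, and it is why the point is an inconsistency and not a gap. It does not rescue the 3-month figure, which either sets a limit that is too short or has no effect.

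A second reply is that contraception periods and outcome follow-up serve different purposes and need not be equal, and that none of the nine 6-month statements concerns outcome follow-up. Section 6.6.1 also places a timed sentence beside an untimed one, so that pattern alone is ordinary drafting here. Both observations are fair. However, in 6.6.1 the timed window equals the restriction period, and the protocol offers no reason for men to be handled differently.

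A third reply is that changing the number leaves the untimed sentences broader than the timed one. That is true. After the change, though, no part of the male precaution period would lie outside the timed rule.

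Section 9.3 suggests that the figure may have practical force. After the final PFS data cut-off it ties completion of the pregnancy forms to the reporting timelines in 6.6. That could mean the deadlines for notifying the sponsor, so it is support and not proof.

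**Conclusion.** The concern holds, at minor severity. The last sentence of 6.6.2 is out of line with its own section's first sentence and with the eight other 6-month statements in inclusion criterion 12, section 3.7.2 and Appendix E. The difference is 3 months of post-treatment exposure for men and none for women.

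The consequence is possible uneven documentation of partner-pregnancy outcomes between sites, not a certain loss of data. The timed sentence concerns the outcomes of known partner pregnancies and does not alter how pregnancies are found. No efficacy analysis, eligibility rule or dosing rule is affected. That the numbers are small is an assumption, since the documents do not give the share of male patients.

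**What to change.** In the last sentence of 6.6.2, replace 3 months with 6 months after the last dose. Inclusion criterion 12, section 3.7.2 and Appendix E already give 6 months and need no edit for this point. Removing or merging the untimed sentence that precedes the timed one would be a further tidy-up, but it is not needed to bring the timed rule into line.

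The cost is one phrase in the protocol and, at most, a very small number of additional partner-pregnancy outcomes to document, each still subject to the partner's consent.

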6.7 Medication Error

For the purposes of this clinical study a medication error is an unintended failure or mistake in the treatment process for an AstraZeneca study drug that either causes harm to the patient or has the potential to cause harm to the patient.

A medication error is not lack of efficacy of the drug, but rather a human or process related failure while the drug is in control of the study site staff or patient.

Medication error includes situations where an error:

- occurred.

- was identified and intercepted before the patient received the drug.
- did not occur, but circumstances were recognize that could have led to an error.

Examples of events to be reported in clinical studies as medication errors:

- Drug name confusion.
- Dispensing error eg, medication prepared incorrectly, even if it was not actually given to the patient.
- Drug not administered as indicated, for example, wrong route or wrong site of administration.
- Drug not taken as indicated eg, tablet dissolved in water when it should be taken as a solid tablet.
- Drug not stored as instructed eg, kept in the fridge when it should be at room temperature.
- Wrong patient received the medication (excluding IVRS/IWRS errors).
- Wrong drug administered to patient (excluding IVRS/IWRS errors).

Examples of events that **do not** require reporting as medication errors in clinical studies:

- Errors related to or resulting from IVRS/IWRS - including those which lead to one of the above listed events that would otherwise have been a medication error.
- Patient accidentally missed drug dose(s) eg, forgot to take medication.
- Accidental overdose (will be captured as an overdose).
- Patient failed to return unused medication or empty packaging.
- Errors related to background and rescue medication, or standard of care medication in open label studies, even if an AstraZeneca product.

Medication errors are not regarded as AEs but AEs may occur as a consequence of the medication error.

If a medication error occurs in the course of the study, then the Investigator or other site personnel informs the appropriate AstraZeneca representatives within 1 day ie, immediately but **no later than 24 hours** of when he or she becomes aware of it.

The designated AstraZeneca representative works with the Investigator to ensure that all relevant information is completed within 1 or 5 calendar days if there is an SAE associated with the medication error (see Section 6.4) and within 30 days for all other medication errors.

6.8 Management of IP related toxicities, Dose reductions

Any toxicity observed during the course of the study could be managed by interruption of the dose of study treatment or dose reductions.

Repeat dose interruptions are allowed as required, for a maximum of 3-4 weeks on each occasion (depending on the toxicity and treatment arm). If study treatment cannot be restarted within the specified period, then the patient must permanently discontinue study treatment. If the interruption is any longer, the study team must be informed.

For olaparib, study treatment can be dose reduced to 250 mg bd as a first step and to 200 mg bd as a second step. If the reduced dose of 200 mg bd is not tolerable, no further dose reduction is allowed and study treatment should be discontinued.

Table 9 Dose reductions for olaparib

Initial Dose	Following re-challenge post interruption: Dose reduction 1	Dose reduction 2
300 mg bd	250 mg bd	200 mg bd

No longer applies from CSPv6.0. For AZD1775, only 1 dose reduction will be allowed. Patients requiring >1 dose reduction will be discontinued from the study drug. Only one dose reduction in olaparib is permitted in the AZD1775+olaparib treatment arm.

Table 10 No longer applies from CSPv6.0 - AZD1775+olaparib dose reduction

Dose Level	AZD1775	olaparib
Initial dose, 21-day cycle	150 mg bd D 1-3 and D 8-10	200mg bd continuous
Dose reduction	* Dose reduce either AZD1775 or olaparib or both	
	125 mg bd D 1-3 and D 8-10	150mg bd continuous

*AZD1775 and olaparib may be reduced in a stepwise manner e.g. first event, dose reduce AZD1775; second event, dose reduce olaparib. If a dose reduction is required for neutropenia, leukopenia or thrombocytopenia, dose reduction of AZD1775 should be implemented first. AZD1775 and olaparib may be dose reduced simultaneously depending on the severity of the event. Dose reductions for anaemia should occur for olaparib first (with consideration to a simultaneous dose reduction in AZD1775 depending on the severity, duration and recurrence of the anaemia).

Once a dose is reduced, re-escalation is not permitted. Due to the recommendation to close the AZD1775+olaparib arm in April 2019 patients continuing treatment on the

AZD1775+olaparib treatment arm should be offered the opportunity to escalate the dose of olaparib to 300 mg bd continuing on a 21-day cycle starting at the patient's next treatment cycle. If a patient has had a dose reduction of olaparib due to toxicity on this treatment combination, the investigator may consider a stepwise increment in the olaparib dose at their discretion, e.g. 200 mg, 250 mg then 300 mg. The visit schedule should be followed as per [Table 5](#) at escalation. For patients continuing on olaparib monotherapy at 300 mg bd please follow the toxicity management guidance as per olaparib monotherapy.

For ceralasertib, study treatment can be dose reduced according to the following dose modification table. A maximum of two dose reduction steps are permitted. If after the second dose reduction treatment is not tolerated, no further dose reduction is allowed and study treatment should be discontinued. Once a dose is reduced, re-escalation is not permitted.

Table 11 Ceralasertib+olaparib dose reduction

CCI

Third dose reduction: No further reduction, withdraw patient and treat as clinically indicated.

* Ceralasertib and olaparib may be reduced stepwise within each dose reduction level e.g. dose reduce olaparib first followed by ceralasertib if the adverse event recurs. Dose reductions for anaemia should occur for olaparib first (with consideration to a simultaneous dose reduction in ceralasertib depending on the severity, duration and recurrence of the anaemia). If a dose reduction is required for neutropenia, leukopenia and thrombocytopenia, olaparib and ceralasertib should be dose reduced simultaneously as there is a greater frequency associated with ceralasertib. Once a dose is reduced, re-escalation is not permitted.

6.8.1 Management of haematological toxicity

6.8.1.1 Olaparib monotherapy and ceralasertib combination (includes patients continuing on olaparib monotherapy randomised to the AZD1775+olaparib arm)

Olaparib monotherapy and ceralasertib+olaparib combination: Complete blood counts will be obtained for all patients at Day 1, 7 and 15 in cycle 1, and then at the beginning of each treatment cycle (Day 1). Complete blood counts must be reviewed prior to dose administration. If hematologic toxicity occurs treatment should be modified as below ([Table 12](#) for Day 1 of each cycle and [Table 14](#) observed at any time during the cycle after Day 1)

and ANC and platelets should be monitored weekly (more often as clinically indicated until recovery). For grade 2 and 4 events please also refer to [Table 14](#). If haematologic parameters do not recover within 28 days, the patient should be removed from the study treatment.

Table 12 Day 1 Haematologic dose modifications and management

Treatment day blood counts and toxicity			
ANC		Platelets	Action
≥1,500/μL	And	≥100,000/μL	No dose modification or interruption
<1,500/μL	Or	<100,000/μL	Delay by 1 week intervals until recovery

Table 13 Management of anaemia

Haemoglobin	Action to be taken
Hb <10 but ≥8 g/dL (CTCAE Grade 2)	
Give appropriate supportive treatment and investigate causality.
 
Investigator judgement to continue study treatment with supportive treatment (eg transfusion) or interrupt dose for a maximum of 4 weeks until recovery to grade 1 or better (≥10g/dL).
 
CCI

Hb <8 g/dL (CTCAE Grade 3)	
Give appropriate supportive treatment (eg, transfusion) and investigate causality.
 
Interrupt study treatment for a maximum of 4 weeks until improved to Hb ≥10 g/dL.
 
CCI

Common treatable causes of anaemia (eg, iron, vitamin B12 or folate deficiencies and hypothyroidism) should be investigated and appropriately managed. In some cases management of anaemia may require blood transfusions. For cases where patients develop prolonged haematological toxicity (≥ 2 week interruption/delay in study treatment due to CTCAE grade 3 or worse anaemia and/or development of blood transfusion dependence), refer to Section 6.8.1.4 for management of this.

6.8.1.2 Olaparib monotherapy and ceralasertib combination: Management of neutropenia, leukopenia and thrombocytopenia (includes patients continuing on olaparib monotherapy randomised to the AZD1775+olaparib arm)

Table 14 provides guidance for hematologic toxicity (neutropenia, leukopenia and thrombocytopenia) observed any time during the study treatment period. **For Day 1 of each cycle please check the required blood counts to commence treatment in Table 12.**

Table 14 Management of neutropenia, leukopenia and thrombocytopenia

Toxicity	Study treatment dose adjustment
CTCAE Grade 1-2	Investigator judgement whether to continue treatment or dose interrupt. If dose interrupted this should be for a maximum of 4 weeks. All patient should have appropriate supportive treatment and causality investigation.
CTCAE Grade 3-4	Dose interruption until recovered to CTCAE grade 1 or better for a maximum of 4 weeks. If repeat CTCAE grade 3-4 occurrence, CCI [REDACTED] as a second step.

Adverse events of neutropenia and leukopenia should be managed as deemed appropriate by the Investigator with close follow up and interruption of study drug if CTC grade 3 or worse neutropenia occurs.

If a patient has experienced a Grade 3/4 neutropenia, G4 thrombocytopenia, or a dose interruption due to haematological toxicity in a prior cycle, unscheduled Day 8 and Day 15 complete blood counts are required in subsequent treatment cycles. If no further events are experienced in the subsequent 3 consecutive cycles, then the Day 15 CBC visit can be stopped, see Table 4.

Primary prophylaxis with G-CSF is not recommended, however, if a patient develops febrile neutropenia, study treatments should be stopped and appropriate management including G-CSF should be given according to local hospital guidelines. G-CSF should not be used within 24hrs of the last dose prior to dose interruption. Please note that G-CSF should not be used within 24 h of the last dose of study treatment unless absolutely necessary.

Platelet transfusions, if indicated, should be done according to local hospital guidelines.

For cases where patients develop prolonged haematological toxicity (>2 week interruption/delay in study treatment due to CTC grade 3 or worse), refer to Section 6.8.1.4.

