6.8.1.4 Management of prolonged haematological toxicities while on study treatment

If a patient develops prolonged haematological toxicities such as:

- ≥ 2 week interruption/delay in study treatment due to CTC grade 3 or worse anaemia and/or development of blood transfusion dependence
- ≥ 2 week interruption/delay in study treatment due to CTC grade 3 or worse neutropenia ($ANC < 1 \times 10^9/L$).
- ≥ 2 week interruption/delay in study treatment due to CTC grade 3 or worse thrombocytopenia ($Platelets < 50 \times 10^9/L$) and/or development of platelet transfusion dependence.

Check weekly differential blood counts including reticulocytes and peripheral blood smear. If any blood parameters remain clinically abnormal after 4 weeks of dose interruption, the patient should be referred to haematologist for further investigations. Bone marrow analysis and/or blood cytogenetic analysis should be considered at this stage according to standard haematological practice. Study treatment should be discontinued if blood counts do not recover to CTC grade 1 or better within 4 weeks of dose interruption.

Development of a confirmed MDS or other clonal blood disorder should be reported as an SAE and full reports must be provided by the Investigator to AstraZeneca Patient Safety. Study treatment should be discontinued if patient's diagnosis of MDS and/or AML is confirmed.

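### Protocol Sections 6.8.1.1, 6.8.1.2 and 6.8.1.4 are not consistent on when Table 14 applies, on what platelet recovery means, and on the trigger for prolonged toxicity

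*Protocol*

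**What the plan says.** Section 6.8.1.1 of the protocol covers olaparib monotherapy and ceralasertib+olaparib, including patients from the closed arm who continue on olaparib alone. It gives Table 12 for Day 1 of each cycle and Table 14 for toxicity "observed at any time during the cycle after Day 1". It then adds "For grade 2 and 4 events please also refer to" Table 14. Under Table 12, an ANC below 1,500/μL or platelets below 100,000/μL lead to one action: "Delay by 1 week intervals until recovery". The section closes with the removal rule: "If haematologic parameters do not recover within 28 days, the patient should be removed from the study treatment".

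Section 6.8.1.2 introduces Table 14 as guidance for toxicity "observed any time during the study treatment period", followed by a bold sentence: "For Day 1 of each cycle please check the required blood counts to commence treatment in Table 12". Table 14 leaves Grades 1-2 to the investigator, who may continue or interrupt. For Grades 3-4 it says "Dose interruption until recovered to CTCAE grade 1 or better for a maximum of 4 weeks". The action for a repeat Grade 3-4 event is redacted.

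Section 6.8.1.4, on prolonged toxicity, says "Study treatment should be discontinued if blood counts do not recover to CTC grade 1 or better within 4 weeks of dose interruption".

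Section 6.8 adds a general rule: treatment that cannot be restarted within the specified period must be stopped permanently.

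**The concern.** These sections decide when a dose is held, when it may resume and when a patient comes off treatment. They give two different scopes for Table 14 and two different platelet tests for recovery. Sites could therefore handle the same count differently.

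After cycle 1, Day 1 is the only scheduled blood count unless earlier toxicity has triggered extra counts. Section 1.3.3 names delayed platelet recovery as the main issue with ceralasertib, so any uncertainty about platelet recovery plausibly falls more on the combination arm of an open-label trial. The SAP reports dose interruptions and reductions (4.2.8.8), dose intensity (4.2.8.9) and treatment discontinuation (4.2.10.8) by arm, and these would absorb differences in how sites read the text.

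**Working it through.** No sample-size or power figure is involved. The check applies the printed rules to example counts. Grade limits come from Table 15 and the dosing criterion above it, in Section 6.8.1.3. That section no longer applies to dosing and is used here only for grading. It labels ANC ≥1,500/μL as Grade 1 and starts platelet Grade 2 at 75,000/μL. Its Grade 3 limits (ANC <1,000/μL, platelets <50,000/μL) match those in Section 6.8.1.4.

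**Step 1: Day 1 counts.**

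| Day 1 count (per μL) | Grade | Table 12 | Table 14 | Referred to Table 14 by 6.8.1.1? |
|---|---|---|---|---|
| ANC 1,200 or platelets 60,000 | 2 | Delay | Investigator decides | Yes |
| ANC 800 or platelets 40,000 | 3 | Delay | Interrupt to Grade ≤1; repeat action redacted | Not named |
| ANC 300 or platelets 20,000 | 4 | Delay | Interrupt to Grade ≤1; repeat action redacted | Yes |
| Platelets 90,000 | Below 2 | Delay | Investigator decides, if Grade 1 | No |

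- Grade 2: the two tables differ, and Section 6.8.1.1 points to both.
- Grades 3 and 4: both tables hold the dose. Table 14 treats these grades alike, yet the cross-reference names only Grade 4. It is therefore unclear whether a Grade 3 event found on Day 1 counts towards the repeat-event step.

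**Step 2: recovery thresholds.**

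- ANC: Table 12 limit 1,500; Grade 1 limit 1,500. The gap is 1,500 − 1,500 = 0.
- Platelets: Table 12 limit 100,000; Grade 1 from 75,000. The gap is 100,000 − 75,000 = 25,000/μL.
- Time limit: 28 days against 4 × 7 = 28 days. These agree.

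**Step 3: one patient traced through the rules.** Platelets fall to 40,000/μL (Grade 3) during a cycle and treatment is interrupted. They rise to 80,000/μL and are still there after 4 weeks.

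- Table 14: recovered to Grade 1, so the interruption can end.
- Section 6.8.1.4: recovered to Grade 1, so its discontinuation criterion is not met.
- Table 12: below 100,000/μL, so a cycle cannot start on Day 1.
- Section 6.8.1.1: removed at 28 days if *recover* means the Table 12 limit; not removed by this rule if it means Grade 1.
- Section 6.8: treatment that cannot be restarted in time is stopped permanently.

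**Step 4: referral trigger.** Section 6.8.1.2 refers patients to 6.8.1.4 after an interruption or delay of >2 weeks. Section 6.8.1.4 itself uses ≥2 weeks, as does the anaemia text in 6.8.1.1. An interruption of exactly 2 weeks is treated differently.

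**The case against.** The strongest reply is that the text can be read coherently. Both sections send Day 1 starting counts to Table 12, the second of them in bold, and *also refer* adds Table 14 without displacing Table 12. This largely stands: Table 12 is the natural authority for holding a Day 1 dose. It does not explain why Grade 2 is referred to a table that allows continuing, or why Grade 3 is omitted.

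On recovery, it can be said that Section 6.8.1.4 is only one discontinuation rule, so escaping it does not mean staying on treatment. The restart test in Section 6.8 points the same way as removal under 6.8.1.1. A stricter test for starting a cycle may also be deliberate. These points are fair. But if that is the intention, the Grade 1 test in 6.8.1.4 does not decide the outcome for platelets between 75,000 and <100,000/μL, and the protocol does not say so.

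A reader might also infer that repeat Grade 3 toxicity on Day 1 escapes dose reduction and may be rechallenged at the same dose. The documents do not support this. The repeat action in Table 14 is redacted, and Section 6.8 separately allows dose reduction for any toxicity.

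**Conclusion.** The inconsistency is real but limited to three points: the scope of Table 14 on Day 1, including the omission of Grade 3; the undefined recovery test, for platelets only; and the >2 versus ≥2 week trigger.

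The recovery conflict rests on two assumptions: that the grade limits in the closed-arm section also apply to the active arms, and that the patient entered Section 6.8.1.4 through Grade 3 or worse thrombocytopenia. A patient merely held at 80,000/μL, with neither that history nor platelet transfusion dependence, does not meet the platelet triggers there. Removal under 6.8.1.1 further depends on how *recover* is read.

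A reader might conclude that any abnormal Day 1 count leaves a patient equally open to being delayed or continued, reduced or not, removed or kept. The text does not go that far: Table 12 is named for Day 1 in both sections, the reduction step cannot be read, and neutrophil recovery is defined consistently. Nor is every routine count affected. Counts that meet Table 12 raise no question, and earlier Grade 3/4 neutropenia, Grade 4 thrombocytopenia or a haematological interruption brings Day 8 and Day 15 counts.

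The documents do not give the frequency of such cases, and the effect on PFS is not known. PFS events count regardless of treatment withdrawal (Protocol 8.4.1, SAP 3.3.1). The point still merits correction because it concerns dose-hold and discontinuation instructions that should be read alike at every site.

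**What to change.** Reconcile Sections 6.8, 6.8.1.1, 6.8.1.2 and 6.8.1.4:

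- State once which of Tables 12 and 14 applies to a Day 1 count, and for which grades.
- Correct the cross-reference in 6.8.1.1 so that its grades fit the rows of Table 14, and say whether Day 1 events count towards the repeat Grade 3-4 step.
- Use one definition of recovery in Table 12, Table 14, the 28-day rule and the 4-week rule, or state explicitly where the thresholds are meant to differ and which rule then decides discontinuation.
- Use one prolonged-toxicity trigger.

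The choice of thresholds and actions belongs to the sponsor. The cost is clarification wording, with no added visits or samples.
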